Following single SC administration of REMD-477 in healthy subjects, REMD-477 was slowly absorbed, with C_{max} observed at median T_{max} of 4 to 5 days post-dose. Exposure, as assessed by C_{max} and AUC_{0-inf} , increased more than dose-proportionally between the 0.3- and 2.5 mg/kg dose range. The effective half-life was approximately 2 weeks across dose groups. Mean residence time (MRT_{0-t}) increased with increasing dose and reached 317 ± 63 hours at 2.5 mg/kg SC. Following IV administration of REMD-477 at 0.3 mg/kg, the C_{max} was between the C_{max} values from the 1 and 2.5 mg/kg SC cohorts. Exposure based on AUC for the 0.3 mg/kg SC dose group was approximately 25% of that achieved for the corresponding IV dose group.

Phase-1 Study T1DM: R477-101

Protocol R477-101 is a randomized, placebo-controlled, double-blind study to evaluate safety, tolerability and pharmacodynamics of REMD-477 in subjects who have Type 1 diabetes and are currently receiving insulin treatment. This proof of concept study evaluated whether glucagon receptor blockade using a single dose 70 mg SC of REMD-477 could decrease insulin requirements and improve glucose homeostasis versus placebo in patients with Type 1 diabetes. The study was completed in January, 2017.

Patients were admitted to an inpatient facility and evaluated over the course of 5 days. Insulin requirements to achieve tight glycemic control was determined on Day 1. On Day 2, insulin infusions were reduced to increase glucose levels to 250-300 mg/dL and REMD-477 or placebo was injected. On Days 3 and 4, insulin was then adjusted to maintain glycemic control similar to that achieved on Day 1. Continuous glucose monitoring was conducted throughout the study to evaluate glucose fluctuation, average glucose concentration, and percentage of time in range (70-180 mg/dL), percentage of time with low glucose concentrations (<70 mg/dL), and percentage of time with high glucose concentrations (>180 mg/dL).

A total of 21 patients were enrolled. Based on preliminary review of safety data review in January 2017, a single dose of 70 mg SC REMD-477 was safe and well-tolerated. There were

no significant drug related adverse events. No deaths, dose limiting toxicities or withdrawals due to adverse events have been reported. No notable changes in ECG, safety lab tests, or vital signs were reported. One patient whose treatment assignment remains blinded experienced an increase in ALT that was less than 1.6 times the upper limit of the laboratory normal on Days 22 and 50 after a single SC injection. There was no corresponding increase in bilirubin or alkaline phosphatase. The elevation occurred 21 and 49 days after administration of treatment which is not consistent with previous observations for liver enzyme increases in both healthy subjects and Type 2 diabetics which usually occur between 4-14 days after drug administration. No severe hypoglycemia was reported in the study patients.

An interim analysis of the first 17 subjects found REMD-477 treatment reduced daily insulin use by 32% (4.2%, 60%) vs. placebo on Day 4 ($p=0.027$). Average daily glucose assessed by CGM was 19 mg/dL (6.2, 31; $p=0.006$), and 26 mg/dL (8.2, 45; $p=0.008$) lower in the REMD-477 group than in the placebo group at Weeks 2 and 3 after treatment, respectively. Glucose time-in-range (70-180 mg/dL) for REMD-477 was 9.5% (2.7%, 16%; $p=0.009$) and 13% (1.9%, 25%; $p=0.026$) greater in the REMD-477 group than in the placebo group during Weeks 2 and 3 after treatment, respectively.

Phase-1b-2a Study T2DM: R477-201

Protocol R477-201 is a randomized, placebo-controlled, double-blind, dose escalation study to evaluate safety, tolerability, PK and PD of single and repeated SC doses of REMD-477 in Type 2 diabetic subjects. The ongoing study includes a dose escalation phase (Part A) followed by an adaptive dose cohort phase (Part B) and two additional cohorts testing REMD-477 in combination with metformin (Part C).

In Parts A and B, approximately 72 subjects will be enrolled with Type 2 diabetes who are either treatment-naïve, controlled with diet and exercise or treated with oral antidiabetic medications. As of February 2017, 60 of subjects have been enrolled across 5 dose cohorts at dose levels of 14 mg, 28 mg, 35 mg, 42 mg, and 70 mg. Each cohort included 9 patients treated with REMD-477 and 3 treated with placebo. Patient received a single SC injection and 28 day observation followed by 8 weekly SC injections.

Part C of this study will enroll approximately 30 subjects with Type 2 diabetes who are currently on stable doses of metformin for at least 8 weeks. Each cohort will include 10 patients treated with REMD-477 and 5 treated with placebo. Patients will receive 12 weekly SC injections.

As of March 2017, the safety and tolerability of REMD-477 (multiple doses up to 70 mg SC) is available in 48 patients with T2DM. There are no significant drug related adverse events. No deaths, dose limiting toxicities or withdrawals due to adverse events have been reported. No notable changes in ECG or vital signs were reported. Importantly, there was no evidence of increased blood pressure. Mild reversible elevations of ALT up to 2.5x ULN were observed in 2 of 12 patients in the 42 mg cohort. At 70 mg, ALT increases up to 3x ULN were observed in 7 of 12 patients in the 70 mg cohort with a single isolated elevation of 18x ULN in one patient at one time-point that decreased below the ULN with continued dosing. Transaminase elevations were not associated with bilirubin or alkaline phosphatase increases. There were no other notable safety lab abnormalities observed. No hypoglycemia was observed across all dose cohorts.

Based on preliminary analysis, fasting glucose decreased 45-52 mg/dL relative to baseline after multiple doses of 14 mg to 42 mg while placebo treatment was associated with a decrease up to 10 mg/dL. Glucose AUC also decreased 130-172 h*mg/dL relative to baseline in the REMD-477 group versus placebo which showed decreases up to 39 h*mg/dL. HbA1c was evaluated at Days 57, 85, and 141 and showed a maximum decrease of 0.28%, 0.58%, and 1% for 14, 28, and 42 mg groups, respectively versus an increase of 0.03% for the placebo group.

Phase-1 b-2a Study T2DM: REMD-477-201 – Clinical Pharmacokinetics

Detailed plasma concentration over time profiles for REMD-477 were obtained at dose levels between 14 mg and 70 mg after the first and last SC injection. Consistent with results in healthy subjects (FIH Study 20060310), exposure, as assessed by C_{max} and AUC_{0-inf} , increased more than dose-proportionally between the 14 mg and 70 mg dose range. The effective half-life after single and multiple dosing was approximately 1 week across dose groups. Geometric mean accumulation ratio values were 11.2, 29.8, and 12.7 at the 14-, 28-, and 42-mg dose levels, respectively, indicating significant accumulation of REMD-477 after multiple dosing.

Dose Selection Rationale

The proposed dose design for the current study is for subjects to be randomized in a 1:1:1 fashion into one of three treatment groups (placebo, 35 mg REMD-477, or 70 mg REMD-477). Subjects will receive once weekly SC injections of investigational product for 12 weeks and be followed for an additional 12 weeks during washout in the Safety Follow-up Period. In

the subjects with Type 2 diabetes, increasing dose and exposure from 14 mg to 42 mg was associated with reduction in HbA1c. Based on available unblinded interim data, the maximum HbA1c reduction of 1% was achieved at 42 mg after 8 repeated weekly doses. In a blinded evaluation of the 70 mg cohort safety data, ALT increases were observed in a greater number of subjects relative to previous lower dose cohorts. In contrast, a single SC dose of 70 mg REMD-477 was not associated with significant increases in ALT in subjects with Type 1 diabetes. Only one subject who received blinded treatment had elevated ALT that were up to 1.6x ULN.

After a single dose of 70 mg of REMD-477 in subjects with Type 1 diabetes, significant reductions in insulin, average glucose, and time in range after CGM were observed. With repeated weekly dosing, substantial (10-30x) accumulation of REMD-477 is expected.

Based on the above findings, dose levels of 35 mg and 70 mg administered once weekly by SC injection over 12 weeks are being proposed. At these dose levels, significant improvements in glycemic control and reduction in insulin requirements are expected after multiple dosing. In addition, minimal to no transaminase elevations are expected based on the findings in Type 1 diabetics after a single 70 mg dose and the manageable transaminase elevations in Type 2 diabetics.

Hypothesis

Multiple doses of REMD-477 will significantly decrease daily insulin use versus placebo treatment at Week 12.

3. EXPERIMENTAL PLAN

Study Design

This is a randomized, placebo-controlled, double-blind study to evaluate the efficacy, safety, and PD of multiple doses of REMD-477 in subjects who have Type 1 diabetes and are currently receiving insulin treatment. This study will determine whether glucagon receptor blockade with REMD-477 can improve HbA1c after 12 weeks of treatment in subjects diagnosed with Type 1 diabetes and with fasting C-peptide < 0.7 ng/mL at Screening.

The two part study (Parts A and B) will be conducted at multiple sites in the United States. In each part, approximately 75 subjects (150 subjects across Parts A and B) with Type 1 diabetes on stable doses of insulin will be randomized in a 1:1:1 fashion into one of three treatment groups (placebo, 35 mg REMD-477, or 70 mg REMD-477). The enrollment of Part B may be initiated prior to the completion of Part A. Subjects will receive once weekly SC injections of investigational product for 12 weeks and be followed for an additional 12 weeks during washout in the Safety Follow-up Period. At baseline, throughout the treatment period, and during the 12-week Safety Follow-up Period, subjects will be evaluated for measures of glycemic control, daily insulin requirements, and safety. For subjects enrolled in Parts A and B, CGM and seven-point glucose profile will be conducted to assess the effect of REMD-477 versus placebo on glucose variability and metabolic control. For a subset of subjects in Part A who were enrolled prior to Protocol Amendment #1, beta cell function after mixed meal and arginine challenge will be examined. For subjects in Part A, alpha cell function will be assessed by measuring fasting glucagon, active and total glucagon-like peptide 1 (GLP-1), and glucagon and GLP-1 (active and total) AUC after the MMTT.

For a subset of subjects in Part A who were enrolled prior to Protocol Amendment #1, eligible subjects will be admitted to the clinical research unit (CRU) on the evening of the Baseline Overnight Visit (which can occur between Study Day -8 to Day -2), the Week 13 Visit (admission Day 84), and the Week 24 Visit (admission Day 161). For ongoing subjects at time of the Protocol Amendment #1, the overnight admissions to the CRU at Baseline, Week 13 and Week 24 will not occur.

For a subset of subjects in Part B, the magnetic resonance imaging – proton density fat fraction (MRI-PDFF) and FibroScan® (where feasible) will be performed prior to dosing on Day 1 (or up to

7 days prior to the Day 1 visit, after all other inclusion and exclusion criteria have been met) and on Day 85 (+/- 2 days) of Week 13.

Number of Centers

This study will be conducted at multiple (approximately 7 - 8) research centers in North America.

Number of Subjects

Approximately 150 subjects (75 in Part A and 75 in Part B) with Type 1 diabetes on stable doses of insulin will be randomized in a 1:1:1 fashion into one of three treatment groups (placebo, 35 mg REMD-477, or 70 mg REMD-477). Subjects will be enrolled in only one treatment group of the study.

Replacement subjects may be enrolled as per the Principal Investigator or REMD Biotherapeutics' discretion.

The sample size justification for subjects enrolled in this study is provided in Section 10 – Statistical Consideration.

Estimated Study Duration

Study Duration for Participants

Including the 42-day screening period, Lead-in Period of up to 4 weeks, study drug treatment period of 84 days and a safety follow-up period of 84 days, the maximum subject participation time is approximately 232 days.

End of Study

End of study is defined as having completed study procedures up to and including Day 162. Subjects who withdraw from study participation prior to the EOS visit date should complete EOS assessments and the early termination date will be the date of the final clinical evaluation.

4. SUBJECT ELIGIBILITY

Investigators will maintain a screening log of all potential study candidates that includes limited information about the potential candidate (age, sex, race), date, and outcome of the screening process (e.g., enrolled into study, reason for ineligibility, or refused to participate).

Inclusion Criteria:

1. Men and women between the ages of 18 and 65 years old, inclusive, at the time of screening;
2. Females of non-child bearing potential must be \geq 1 year post-menopausal (confirmed by a serum follicle-stimulating hormone (FSH) levels \geq 40 IU/mL) or documented as being surgically sterile. Females of child bearing potential must agree to use two methods of contraception during the entire study and for an additional 3 months after the end of dosing with the investigational product;
3. Male subjects must be willing to use clinically acceptable method of contraception during the entire study and for an additional 6 months after the end of the treatment period;
4. Body mass index between 18.5 and 32 kg/m², inclusive, at screening (note that the subject's total daily insulin should be \leq 1.0 unit/kg);
5. Diagnosed with Type 1 diabetes based on clinical history or as defined by the current American Diabetes Association (ADA) criteria;
6. HbA1c $>$ 7% and $<$ 10% at screening;
7. Fasting C-peptide $<$ 0.7 ng/mL;
8. Treatment with a stable insulin regimen for at least 8 weeks before screening with multiple daily insulin (MDI) injections or continue subcutaneous insulin infusion (CSII)
9. Willing to use study-dedicated Continuous Glucose Monitoring (CGM) system (e.g. DexCom) throughout the study, subjects may continue to use personal CGM systems during the study but must be on stable use for at least 3 months prior to Screening;
10. ALT and/or AST \leq 1.5x ULN at screening;

11. Able to provide written informed consent approved by an Institutional Review Board (IRB).

Exclusion Criteria:

1. History or evidence of clinically-significant disorder or condition that, in the opinion of the Investigator, would pose a risk to subject safety or interfere with the study evaluation, procedures, or completion;
2. Significant organ system dysfunction (e.g., clinically significant pulmonary or cardiovascular disease, anemia [Hemoglobin < 10.0 g/dL], known hemoglobinopathies, and renal dysfunction [eGFR < 60 ml/min]);
3. Any severe symptomatic hypoglycemic event associated with a seizure or requiring help from other people or medical facility in the past 6 months;
4. Myocardial infarction, unstable angina, revascularization procedure, or cerebrovascular accident ≤ 12 weeks before screening;
5. History of New York Heart Association Functional Classification III-IV cardiac disease;
6. Current or recent (within 1 month of screening) use of diabetes medications other than insulin – subjects on an SGLT2 inhibitor should discontinue the SGLT2 inhibitor during the Screening Period, at least 2 weeks prior to the start of the Lead-in Period;
7. Use of steroids and/or other prescribed or over-the-counter medications that are known to affect the outcome measures in this study or known to influence glucose metabolism;
8. Smokes > 10 cigarettes/day and/or is unwilling to abstain from smoking during the admission periods;
9. Known sensitivity to mammalian-derived drug preparations, recombinant protein-based drugs or to humanized or human antibodies;
10. History of illicit drug use or alcohol abuse within the last 6 months or a positive drug urine test result at screening;
11. History of pancreatitis, pancreatic neuroendocrine tumors or multiple endocrine

neoplasia (MEN) or family history of MEN;

12. History of pheochromocytoma, or family history of familial pheochromocytoma;
13. Known or suspected susceptibility to infectious disease (e.g. taking immunosuppressive agents or has a documented inherited or acquired immunodeficiency);
14. Known history of positive for human immunodeficiency virus (HIV) antibodies, hepatitis B surface antigen (HbsAg), or hepatitis C antibodies (HepC Ab);
15. Participation in an investigational drug or device trial within 30 days of screening or within 5 times the half-life of the investigational agent in the other clinical study, if known, whichever period is longer;
16. Blood donor or blood loss > 500 mL within 30 days of Day 1;
17. Women who are pregnant or lactating/breastfeeding;
18. Unable or unwilling to follow the study protocol or who are non-compliant with screening appointments or study visits;
19. Any other condition(s) that might reduce the chance of obtaining study data, or that might cause safety concerns, or that might compromise the ability to give truly informed consent.

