4. Body mass index between 18.5 and 32 kg/m², inclusive, at screening (note that the subject's total daily insulin should be ≤ 1.0 unit/kg);
5. Diagnosed with Type 1 diabetes, based on clinical history or as defined by the current American Diabetes Association (ADA) criteria;
6. HbA1c $> 7\%$ and $< 10\%$ at screening;
7. Fasting C-peptide < 0.7 ng/mL;
8. Treatment with a stable insulin regimen for at least 8 weeks before screening with multiple daily insulin (MDI) injections or continue subcutaneous insulin infusion (CSII);
9. Willing to use study-dedicated Continuous Glucose Monitoring (CGM) system (e.g. DexCom) throughout the study; subjects may continue to use personal CGM systems during the study but must be on stable use for at least 3 months prior to screening.
10. ALT and/or AST $\leq 1.5\times$ ULN at screening;
11. Able to provide written informed consent approved by an Institutional Review Board (IRB).

Exclusion Criteria:

1. History or evidence of clinically-significant disorder or condition that, in the opinion of the Investigator, would pose a risk to subject safety or interfere with the study evaluation, procedures, or completion;

2. Significant organ system dysfunction (e.g., clinically significant pulmonary or cardiovascular disease, anemia [Hemoglobin < 10.0 g/dL], known hemoglobinopathies, and renal dysfunction [eGFR < 60 ml/min]);
3. Any severe symptomatic hypoglycemic event associated with a seizure or requiring help from other people or medical facility in the past 6 months;
4. Myocardial infarction, unstable angina, revascularization procedure, or cerebrovascular accident ≤12 weeks before screening;
5. History of New York Heart Association Functional Classification III-IV cardiac disease;
6. Current or recent (within 1 month of screening) use of diabetes medications other than insulin – subjects on an SGLT2 inhibitor should discontinue the SGLT2 inhibitor during the Screening Period, at least 2 weeks prior to the start of the Lead-in Period;
7. Use of steroids and/or other prescribed or over-the-counter medications that are known to affect the outcome measures in this study or known to influence glucose metabolism;
8. Smokes > 10 cigarettes/day, and/or is unwilling to abstain from smoking during admission periods;
9. Known sensitivity to mammalian-derived drug preparations, recombinant protein-based drugs or to humanized or human antibodies;

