Study recruitment, progress and safety issues will be reviewed by the investigators, research nurse and research coordinators and communicated to the sponsor on a regular basis. The following will be reviewed: 1) subject enrollment, 2) preliminary findings that might affect the risk/benefit ratio or alter the procedures described in the protocol, 3) any clinically-significant out-of-range laboratory value and a course of action, and 4) any adverse or serious adverse events that might result from the research procedures.

The Safety Review Committee will review all available safety and PD data periodically during the study when approximately 33%, 66%, and 100% of the subjects in Part A have received a randomized treatment. After each safety data review, the Safety Review Committee will decide whether or not to continue with subject enrollment and dosing. Decisions to continue enrollment will be documented in the Safety Review Memo. REMD Biotherapeutics will issue a written notification of these decisions to investigators.

Determination of Adverse Event Severity and Relatedness

Adverse events will be coded per current MedDRA. Determination of the severity of adverse events will be consistent with Common Terminology Criteria for Adverse Events (CTCAE) V. 4.03. The relationship of an adverse event to treatment will be determined by the Investigator (see section 9: Reporting Procedures for All Adverse Events).

Dose Stopping Rules

Dosing will be stopped or modified if treatment-related AEs, changes in vital signs, ECG, or clinical laboratory results are observed and these changes pose a significant health risk, in the opinion of the Sponsor, Principal Investigator or Medical Monitor.

Medically significant AEs considered to be related to the investigational product and serious adverse events considered to be related to study procedures will be followed until resolved or considered stable.

A subject may be terminated at any point in time at the discretion of the Sponsor, Principal Investigator or Medical Monitor.

Stopping Rules for an Individual Subject:

At any time during the study, the subject must discontinue study drug treatment, if one of the following events occur:

- An increase of AST and/or ALT (> 3x ULN) are observed in the presence of increased (> 2x ULN) alkaline phosphatase and/or total bilirubin.
- A sustained AST or ALT increase, defined as three consecutive values of AST and/or ALT greater than 5x ULN within a period of 14 days.

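### Inclusion criterion 10 can be met with only one of ALT and AST within 1.5x ULN, leaving the other enzyme without a numeric limit at entry

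*Protocol*

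**What the plan says.** Protocol Section 4, inclusion criterion 10, reads "ALT and/or AST \leq 1.5x ULN at screening". The Synopsis has the same line, "ALT and/or AST $\leq 1.5\times$ ULN at screening", so neither place settles the meaning of the other.

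No other inclusion or exclusion criterion gives a numeric limit for ALT, AST or bilirubin. Three exclusions could bear on a subject with a raised enzyme:

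- Exclusion 1 covers a disorder that "in the opinion of the Investigator, would pose a risk to subject safety or interfere with the study evaluation".
- Exclusion 2 begins "Significant organ system dysfunction (e.g., clinically significant pulmonary or cardiovascular disease, anemia". Its examples give cut-offs for hemoglobin and eGFR but do not mention the liver.
- Exclusion 19 is general: "Any other condition(s) that might reduce the chance of obtaining study data, or that might cause safety concerns".

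The background (Protocol Section 2, study R477-201) reports "Mild reversible elevations of ALT up to 2.5x ULN were observed in 2 of 12 patients in the 42 mg cohort" and "ALT increases up to 3x ULN were observed in 7 of 12 patients in the 70 mg cohort", with one isolated value of 18x ULN.

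Among the individual stopping rules in Protocol Section 6, the first begins "An increase of AST and/or ALT (> 3x ULN) are observed in the presence of increased" and adds a condition on alkaline phosphatase or bilirubin. The second needs three values in a row above 5x ULN inside 14 days. SAP 10.4.2 counts subjects whose ALT or AST exceeds 3x, 5x and 10x ULN after dosing. None of these refers to the subject's own baseline.

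**The concern.** Joining two enzymes with and/or works when either one being high should trigger something, as in a stopping rule or an exclusion. In an inclusion criterion with an upper limit, the effect reverses: one compliant enzyme satisfies the line, whatever the other one shows. A subject with ALT well above 1.5x ULN and AST within it meets the criterion as written.

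Two things are at stake. First, with 7 to 8 centers, some may require both enzymes to comply and others only one, so the entry standard would differ by site. Second, a subject already raised at screening could be dosed with a drug whose earlier studies showed transaminase rises. That subject starts nearer to, or beyond, the ULN-based thresholds used for stopping and for the safety tables, before any drug effect.

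**Working it through.** The plan states no figure on this point, so there is none to reproduce. The check is one of logic, followed by simple arithmetic.

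**Step 1: the two readings.** Let A mean ALT at or below 1.5x ULN, and B mean AST at or below 1.5x ULN. The literal reading is A or B, or both. The strict reading is A and B. The enzyme values below are illustrative assumptions in multiples of ULN.

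| ALT | AST | Literal (at least one) | Strict (both) |
|---|---|---|---|
| 1.0 | 1.0 | eligible | eligible |
| 1.5 | 1.5 | eligible | eligible |
| 2.9 | 1.0 | eligible | not eligible |
| 1.0 | 2.9 | eligible | not eligible |
| 6.0 | 1.4 | eligible | not eligible |
| 2.9 | 2.9 | not eligible | not eligible |

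The readings differ exactly when one enzyme is above 1.5x ULN and the other is not. In those cases the literal text puts no ceiling on the raised enzyme. Values between 1x and 1.5x ULN are allowed under both readings, so the issue concerns values above 1.5x ULN only.

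**Step 2: distance to the 3x ULN threshold.** A subject entering at the limit must rise by a factor of 3/1.5 = 2 to reach 3x ULN. A subject entering at 2.9x needs a factor of 3/2.9 = 1.03. A subject entering at 6.0x and staying there is counted above 3x and above 5x ULN with no change at all.

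**Step 3: weight of one subject.** The protocol and SAP Section 8 plan 25 per group in each part, and SAP 10.1 produces outputs separately for Parts A and B. One subject is 1/25 = 4 percentage points of an arm's rate.

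**Step 4: how prominent the signal is.** The earlier rates (Protocol Section 2) are:

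- R477-201, 70 mg cohort: 7/12 = 58%.
- R477-201, 42 mg cohort: 2/12 = 17%.
- First-in-human study, ALT increase reported as treatment related: 2/30 = 7%.

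Each R477-201 cohort of 12 contained 9 subjects on REMD-477 and 3 on placebo, so its rate is for the whole cohort and not for the drug alone. The 70 mg dose is one of the two used in this trial.

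**The case against.** The strongest reply is that unnoticed entry is unlikely. Exclusions 1, 2 and 19 let an investigator refuse such a subject, and the organ list in exclusion 2 is only a set of examples. Exclusions 10 and 14 remove recent alcohol abuse and known hepatitis B or C. Chemistry is repeated at baseline, Section 5 settles eligibility after the baseline evaluations, and Section 7 requires laboratory results to be reviewed before each dose. All of that stands as mitigation. It rests on individual judgement, however, and gives sites no common number, so it does not cure the wording.

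A reader might infer from the stopping rules, where either enzyme is enough, that the sponsor also meant one compliant enzyme to be enough for entry. The documents do not show this. A rule that treats either raised enzyme as a concern fits an intention to limit both at least as well.

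A reader might also infer that such entrants would bias the liver comparison between arms. That does not follow. Subjects are randomized 1:1:1, so raised entrants are expected equally in every arm and add noise. SAP 10.4.2 also summarizes change from baseline in ALT and AST by treatment and timepoint. This partly offsets the problem, but the threshold counts remain unadjusted.

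Finally, Section 2 (Dose Selection Rationale) expects few or no transaminase elevations at these doses. That is an expectation, set beside the reported rises at 70 mg in type 2 diabetes, and it does not make an unclear entry limit harmless.

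**Conclusion.** The criterion, followed as written, admits a subject with one enzyme above 1.5x ULN and sets no numeric limit on that enzyme. No other criterion supplies one. Given the documented transaminase signal and the ULN-based rules and tables, this is worth correcting, although it does not threaten the primary analysis.

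The size is limited: one subject is 4 percentage points of a 25-subject arm in the above-3x-ULN count, as noise and with no expected difference between arms. The number of such entrants cannot be derived from the documents and may be zero. Nothing in them shows that a site has used the literal reading or that such a subject was enrolled. The conclusion rests on the text of the criterion and on the planned arm size.

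**What to change.** In the Synopsis and in Section 4, reword criterion 10 identically so that the sponsor's existing limit clearly applies to each enzyme, for example: *ALT and AST each at or below 1.5x ULN at screening*. The threshold does not change. If one compliant enzyme really was intended, the sponsor should say so explicitly in both places.

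The cost is one phrase in two places, a note to sites, and possibly a few more screen failures where the line had been read loosely. The change helps only subjects not yet enrolled. SAP Section 12 mentions a first interim of Part A as already past, so some subjects entered before any such correction.
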